7.5 Procedures for Discontinuation or Withdrawal of a Participant

The Investigator must discontinue a participant's study participation at any time during the study when the participant meets the study discontinuation criteria described in Section 7.4. In addition, a participant may discontinue their participation without giving a reason at any time during the study. Should a participant's involvement be terminated, the primary criterion for termination must be recorded by the Investigator. In addition, efforts should be made to perform all procedures scheduled for the Early Termination Visit. Discontinued or withdrawn participants may be replaced at the Sponsor's discretion. Participants who withdraw from the study prior to dosing may be replaced.

Page 29 of 64 30 Aug 2022

8.0 CLINICAL TRIAL MATERIAL MANAGEMENT

8.1 Study Medication and Materials

This section contains information regarding all medication and materials provided directly by the Sponsor and/or sourced by other means required by the study protocol, including important sections describing the management of clinical trial material.

8.1.1 Dosage Form, Manufacturing, Packaging, and Labeling

Study drug refers to CVN424 in both suspension and tablet formulations.

In this protocol, the term study medication refers to all or any of the drugs defined below.

8.1.1.1 Investigational Drug

CVN424 Suspension:

The oral suspension drug product will be compounded by an accredited compounding pharmacy, e.g., Infuserve America Inc.

CVN424 oral suspension is prepared by suspending CVN424 drug substance in 2% Methocel, E15 Premium LV Hydroxypropyl Methylcellulose (HPMC)/0.5% Tween 80 vehicle. CVN424 oral suspension is supplied to the clinical site in bottles with contents clearly labeled, along with the appropriate study information and caution statements.

CVN424 Tablet:

Patheon Milton Park UK will manufacture the bulk drug product (150 mg tablets) and bottle it, and Patheon Allentown, US, will perform labeling and distribution of the study drug.

The components of the CVN424 tablet include the CVN424 API, Colloidal Silicon Dioxide, Croscarmellose Sodium, Hydroxypropylcellulose, Magnesium Stearate, Mannitol, and Microcrystalline Cellulose.

The tablets will be packaged in a high-density polyethylene (HDPE) bottle with an induction seal and a child-resistant cap; each bottle will contain 30 tablets.

Ancillary Materials:

Ancillary materials will be provided by either the clinical site and/or the Sponsor based on availability. Unused ancillary materials provided by the Sponsor will be accounted for and disposed of as directed by the Sponsor or their designee.

8.1.2 Drug Storage

All study drug stored at the investigative site must be kept in an appropriate, limited-access, secure place until it is used or returned to the Sponsor or designee for destruction. All study drug must be stored under the conditions specified on the label and remain in the original container until dispensed. A daily temperature log of the drug storage area must be maintained every working day; short excursions are allowed but must be evaluated by the Sponsor.

8.1.3 Dose and Regimen

Prior to dosing initiation, the Investigator or Investigator's designee will instruct the participant on dosing procedures.

All dosing will occur while participants are in the clinic under the supervision of the Investigator or designee and in fed or fasting conditions as outlined in Section 7.3.

The exact time of dose will be recorded in the source documents and on the appropriate eCRF.

The planned sequences to be studied are provided in Table 3.

Table 3 Three-Way Cross-Over Sequences

Sequence	Dosing #1 (Period 1 Day 1)		Dosing #2 (Period 2 Day 1)		Dosing #3 (Period 3 Day 1)
	1 (n=5)	Suspension (fasted)		Tablet (fasted)	
2 (n=6)	Tablet (fasted)		Tablet (fed)		Suspension (fasted)
3 (n=5)	Tablet (fed)	h o u t	Suspension (fasted)	hout	Tablet (fasted)
4 (n=5)	Suspension (fasted)	Was	Tablet (fed)	Wash	Tablet (fasted)
5 (n=5)	Tablet (fasted)		Suspension (fasted)		Tablet (fed)
6 (n=6)	Tablet (fed)		Tablet (fasted)		Suspension (fasted)

8.1.4 Overdose

An overdose is defined as a known, deliberate, or accidental administration of an investigational drug, to or by a study participant, at a dose above that assigned to that individual participant according to the study protocol.

All cases of overdose (with or without associated AEs) will be documented on an Overdose page of the eCRF, in order to capture this important safety information consistently in the database. Cases of overdose without manifested signs or symptoms are not considered AEs. AEs associated with an overdose will be documented on AE eCRF(s) according to Section 9.7.1.

Serious adverse events (SAEs) associated with an overdose should be reported according to the procedure outlined in Section 9.7.2.

In the event of an overdose, supportive measures should be employed as needed, e.g., administration of supportive therapy as dictated by the participant's clinical status, removal of

unabsorbed material from the gastrointestinal tract, or the initiation of additional clinical monitoring.

8.2 Investigational Drug Assignment and Dispensing Procedures

Participants will be assigned to receive a unique randomization number. Study drug will be dispensed to participants as either tablets or suspensions. The tablets must be stored at controlled room temperature, and the suspensions must be stored refrigerated. See Pharmacy Manual for specifics.

8.3 Randomization Code Creation and Storage

The Sponsor or their designee will generate the randomization schedule and provide a copy to the site pharmacist and bioanalytical laboratory prior to the start of the study. All randomization information will be stored in a secured area.

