6.0 STUDY DESIGN AND DESCRIPTION

6.1 Study Design

This is a randomized, open-label, single-oral dose, three-way cross-over study under fasted and fed conditions, study in healthy participants.

Table 1 Study Schema

Sequence	Dosing #1		Dosing #2		Dosing #3	
	(Period 1 Day 1)		(Period 2 Day 1)		(Period 3 Day 1)	
1 (n=5)	Suspension (fasted)		Tablet (fasted)		Tablet (fed)	
2 (n=6)	Tablet (fasted)		Tablet (fed)		Suspension (fasted)	
3 (n=5)	Tablet (fed)	h o u t	Suspension (fasted)	h o u t	Tablet (fasted)	
4 (n=5)	Suspension (fasted)	Wasl	Tablet (fed)	Wash	Tablet (fasted)	
5 (n=5)	Tablet (fasted)		Suspension (fasted)		Tablet (fed)	
6 (n=6)	Tablet (fed)		Tablet (fasted)		Suspension (fasted)	

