9.1.9 PK Sample Collection

9.1.9.1 Collection of Blood for PK Sampling

Blood samples for analysis of CVN424 plasma concentrations will be collected into chilled Vacutainers containing K₂EDTA.

Instructions for sample processing and shipment are provided in a separate lab manual.

In all sequences, serial blood samples to determine CVN424 concentrations in plasma will be collected according to the Schedule of Study Procedures (Appendix A).

The PK samples will be collected at the nominal time point; all other assessments will be collected, before or after, within the allowable windows. The actual time of sample collection will be recorded on the source document and eCRF.

Sampling time points may be adjusted or added based on the preliminary emerging PK data collected from prior sequence(s).

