9.1.9.3 Bioanalytical Methods

Plasma and urine concentrations of CVN424 will be measured by high-performance liquid chromatography with tandem mass spectrometry using validated (for plasma) and qualified (for urine) assays.

Plasma and urine samples will be archived for potential analysis of metabolites and/or target-related biomarkers, if appropriate.

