5. TREATMENT DESCRIPTIONS

Treatment A will be supplied as 150 mg CVN424 suspension.

Treatments B and C will be supplied as 150 mg CVN424 tablets.

For the Suspension (fasted) and Tablet (fasted) portions: Breakfast will not be provided on dosing days. Participants must fast for a minimum of 4 hours after dose administration unless otherwise indicated. CVN424 will be administered with approximately 240 mL of water after a fast of at least 10 hours. Participants will continue to fast for an additional 4 hours after dosing and eat lunch following the 4-hour PK blood collection. Participants may consume water ad libitum except for 1 hour before and 1 hour after drug administration.

For the Tablet (fed) portion (food effect): CVN424 will be administered after ingesting a standardized high-fat, high-calorie meal according to FDA Guidance for Industry (Foodeffect bioavailability and fed equivalence studies, June 2022). Participants will finish their breakfast in its entirety within 30 minutes and will receive an investigational product 30 minutes (±5 minutes) after beginning the meal. The meal start and stop times, and percentage of the meal consumed will be recorded in the source, and the appropriate case report form (CRF) for all meals served on dosing days.

The treatments descriptions would be described as:

Treatment	Short Description	Long Description
Treatment A	Suspension-Fasted	a single oral dose of 150 mg CVN424 suspension under fasted condition

Treatment	Short Description	Long Description
Treatment B	Tablet-Fasted	a single oral dose of 150 mg CVN424 tablet under fasted condition
Treatment C	Tablet-Fed	a single oral dose of 150 mg CVN424 tablet under fed condition

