6.2 Bioanalytical Method

Plasma and urine concentrations of CVN424 will be determined using high performance liquid chromatography-tandem mass spectrometry (HPLC/MS-MS) method validated with respect to accuracy, precision, linearity, sensitivity, and specificity at Frontage Laboratories, Inc. The analytical range (lower limit of quantitation [LLOQ] – upper limit of quantitation [ULOQ]) for CVN424 in plasma and urine are both expected to be 1 – 1000 ng/mL.

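### Protocol 8.3 gives the bioanalytical laboratory the randomization schedule although no sample is placebo, so assay decisions on the primary-endpoint concentrations could be made with treatment known

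*Protocol*

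**What the plan says.** - **Who receives the schedule.** Under Protocol 8.3, whoever produces the schedule is to "provide a copy to the site pharmacist and bioanalytical laboratory prior to the start of the study". The section adds that the information is stored securely. It does not say who in the laboratory may see it, or why the laboratory needs it. The note to file of 30 September 2022 names the designee that generates the schedule and leaves the recipients as they were.
- **Treatments.** SAP 5: "Treatment A will be supplied as 150 mg CVN424 suspension" and "Treatments B and C will be supplied as 150 mg CVN424 tablets". There is no placebo.
- **Samples.** Protocol 9.1.9.1: "In all sequences, serial blood samples to determine CVN424 concentrations in plasma will be collected". Urine is collected only with tablet-fasted dosing (Protocol 9.1.9.2, SAP 6.3).
- **Assay.** Protocol 9.1.9.3: "Plasma and urine concentrations of CVN424 will be measured by high-performance liquid chromatography with tandem mass spectrometry". That section calls the plasma assay validated and the urine assay qualified. SAP 6.2 places plasma and urine at one laboratory and describes a "method validated with respect to accuracy, precision, linearity, sensitivity, and specificity". Neither section mentions analyst blinding, sample coding, repeat analysis, re-integration or run rejection. Sample processing and shipment are left to a laboratory manual that is not among the documents.
- **Endpoint.** Under SAP 6.4.1, Cmax is read straight from the laboratory's results, and AUC0-96h is computed from the same concentrations by the linear trapezoidal rule.
- **Blinding.** Protocol 6.1: "This is a randomized, open-label, single-oral dose, three-way cross-over study under fasted and fed conditions". Even so, Protocol 11.1 places SAP finalization and a targeted data review before unblinding, and Protocol 12.1 refers to blinding that monitoring must not compromise.

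**The concern.** In a relative bioavailability study the measured concentrations are the primary data. An assay laboratory normally has some discretion: which samples to repeat, whether to re-integrate a peak, whether to reject a run. If the person deciding knows which profile is test and which is reference, that discretion can act on the test/reference ratio. Randomization and the mixed model do not remove an error introduced at measurement.

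A laboratory is sometimes given the schedule so that it need not assay placebo samples. That reason is absent here. Protocol 8.3 is thus a stated rule that gives up a safeguard for no stated benefit.

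The interim looks at plasma data sharpen the point (Protocol 11.2; SAP 6.7, with details in a separate document). A laboratory that holds both the schedule and the early-period concentrations could see the emerging ratio before later periods are assayed.

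**Working it through.** **Step 1: does the laboratory need the schedule?**

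| Possible reason | What the documents say | Result |
|---|---|---|
| To skip placebo samples | All treatments are active (SAP 5) | Does not apply |
| To know which plasma to assay | Plasma is sampled in every sequence (Protocol 9.1.9.1) | Does not apply |
| To know which periods should yield urine | Urine with tablet-fasted dosing only (Protocol 9.1.9.2); its period varies by sequence (Protocol Table 1) | A real reconciliation need, but a site shipping manifest meets it |

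**Step 2: is the laboratory guarded in another way?** Protocol 8.3 mentions secure storage only. Protocol 9.1.9.3 and SAP 6.2 are silent on analyst access. The laboratory manual may restrict access, but it is not available to check.

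**Step 3: reproduce the plan's sample size.** Inputs from Protocol 11.3: within-participant CV 16%, expected ratio 1.10, 28 evaluable of 32 enrolled. (The Study Summary prints the ratio as 1:10; 1.10 is used here.) From SAP 6.6: limits 80.00 to 125.00%, and a 90% CI, equivalent to two one-sided tests at 0.05. The power target is not stated.

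- σ_w = √ln(1 + 0.16²) = √ln(1.0256) = 0.159
- SE = σ_w × √(2/28) = 0.159 × 0.2673 = 0.0425
- Residual df for three periods = 2N − 4 = 52
- Power is the probability that both one-sided tests reject, integrated over the residual variance.

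Power at N = 28 is 0.907 with 52 df, and 0.900 with the two-treatment df of 26. The smallest N reaching 90% is 28 under both choices. At 80% it would be 20 to 21, and at 85% 23 to 24. So 28 reproduces if the target was 90%, which is an assumption. With 12.5% loss, 28/0.875 = 32 = 4×5 + 2×6.

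**Step 4: how sensitive is the conclusion to a shift in the ratio?** The documents give no repeat rate and no size of effect, so every shift below is assumed. One way to reach 0.5 to 1%: if 5 to 10% of tablet profiles moved by 10%, all in one direction, then 0.05 × 10% = 0.5% and 0.10 × 10% = 1%.

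| Assumed shift | Ratio | Power (N = 28, 52 df) |
|---|---|---|
| −2% | 1.078 | 0.964 |
| −1% | 1.089 | 0.940 |
| 0 | 1.100 | 0.907 |
| +1% | 1.111 | 0.863 |
| +2% | 1.122 | 0.806 |

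If the true ratio were at the limit of 1.25, a downward bias of 0, 1, 2 or 3% would give a false conclusion of similar bioavailability with probability 0.050, 0.079, 0.120 or 0.174.

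The 10% movement is generous for AUC0-96h. There are 17 post-dose samples, and repeating one would usually move the area far less. Cmax rests on a single sample and is more exposed.

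**The case against.** The case on the other side is substantial.

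- **Access is not practice.** A reader might infer that repeat and integration decisions are in fact made with treatment known. The documents do not say so. They do not describe who makes those decisions, who in the laboratory opens the schedule, or how tubes are labeled. This stands.
- **The trial is open-label and the plasma assay is validated.** Validation narrows discretion without removing it. The open-label design concerns what participants and site staff know and does not require the laboratory to know treatment. This limits the concern but does not answer it.
- **Urine may justify access.** Reconciliation is a plausible reason, though none is given. A manifest serves equally well, so this does not establish a need for the schedule.
- **Withholding the schedule would not fully blind the laboratory.** Every sequence contains tablet-fasted once, and only that period yields urine. Urine labeled by participant and period would therefore identify the test arm of the primary comparison. Fed profiles may also be recognizable, because the earlier healthy-volunteer study found a later and lower peak after a meal (Protocol 4.1). This stands, and the remedy has to deal with the urine.
- **The size is assumed.** This stands: Step 4 shows sensitivity and estimates nothing.

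**Conclusion.** The point holds as an unguarded and avoidable risk. Protocol 8.3 sends the schedule to the laboratory before the study, no documented task requires it, and nothing supplied keeps it from the analysts who produce the primary-endpoint concentrations. It is a design choice worth changing. It is neither a contradiction nor an error of calculation.

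Two stronger readings should be resisted. A reader might take the power and error figures as the expected damage, but they rest on assumed shifts, all in one direction, and on one CV of 16% applied to both Cmax and AUC. A reader might also conclude that the laboratory is the only party who could be kept unaware of treatment. Protocol 11.1 speaks of work done before unblinding, so the protocol itself contemplates others.

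The right label is a cheap improvement. The planned 28 evaluable participants, the 32 enrolled and the alpha level are unaffected.

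**What to change.** 1. In Protocol 8.3, remove the bioanalytical laboratory as a recipient of the schedule, or limit its copy to a custodian who takes no part in the assays.
2. State that assay analysts do not see the schedule until the concentrations for each period are final, and apply the same rule to the interim analyses.
3. Reconcile samples, including urine, against a site shipping manifest instead of the schedule.
4. Code urine separately from plasma, or assay it after plasma concentrations are final, so that its arrival does not mark the tablet-fasted period.

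The cost is a short change to Protocol 8.3 and minor sample-coding and sequencing work in the laboratory manual. Blinding will remain partial, because fed profiles may still be recognizable. Participant procedures, sample size and the statistical model do not change.

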8.4 Accountability and Destruction of Sponsor-Supplied Drugs

Drug supplies will be counted and reconciled at the site before being returned to the Sponsor or designee or before being destroyed.

The Investigator or designee must ensure that the study medication is used in accordance with the approved protocol and is dispensed only to participants enrolled in the study. To document the appropriate use of study medication, the Investigator must maintain records of all study medication delivery to the site, site inventory used by each participant, and return to the Sponsor or designee.

Upon receipt of study medication, the Investigator or designee must verify the contents of the shipments against the packing list, ensure the quantity is correct, and the medication is received within the labeled storage conditions. If quantity and conditions are acceptable, the Investigator or designee should acknowledge the receipt of the shipment by signing the bottom half of the packing list and send via email and per instructions provided on the form. If discrepancies exist between the packing list and the actual product received, the Sponsor must be contacted to resolve the issue. The packing list should be filed in the Investigator's essential document file. The Investigator must maintain 100% accountability for all study medication received and dispensed during their entire participation in the study. Proper drug accountability includes, but is not limited to:

- Continuously monitoring expiration dates
- Frequently verifying that actual inventory matches documented inventory
- Verifying that the log is completed for the drug lot used to prepare each dose
- Verifying that all containers used are documented accurately on the log
- Verifying that required fields are completed accurately and legibly

If any dispensing errors or discrepancies are discovered, the Sponsor must be notified immediately.

The Investigator or designee must record the current inventory of all study medication on a Sponsor-approved drug accountability log. The following information will be recorded at a minimum: protocol number and title, name of the Investigator, site identifier and number,

Page 32 of 64 30 Aug 2022

description of study medication, expiry date, and amount dispensed, including the initials of the person dispensing and receiving the study medication. The log should include all required information as a separate entry for each participant to whom study medication is dispensed.

Prior to site closure or at appropriate intervals, a representative from the Sponsor or its designee will perform clinical study material accountability and reconciliation before clinical study materials are returned to the Sponsor or its designee for destruction or destroyed at the site, as applicable. The Investigator will retain the original documentation regarding clinical study material accountability, return, and/or destruction, and copies will be sent to the Sponsor or designee.

The Investigator will be notified of any expiry date or retest date extension of clinical study material during the study conduct. On expiry date notification from the Sponsor or designee, the site must complete all instructions outlined in the notification, including segregation of expired clinical study material for return to the Sponsor or its designee for destruction.

9.0 STUDY PLAN

9.1 Study Procedures

The following sections describe the study procedures and data to be collected. For each procedure, participants are to be assessed by the same Investigator or site personnel whenever possible. The Schedule of Study Procedures is located in Appendix A.

9.1.1 Informed Consent Procedure

The requirements of the ICF are described in Section 13.2.

A properly signed ICF must be obtained prior to the participant entering the study and before any protocol-related procedures are performed.

9.1.2 Demographics, Medical History, and Medication History Procedure

Demographic information to be obtained will include date of birth, sex, ethnicity, race as described by the participant, smoking status, and caffeine consumption at Screening.

Medical history to be obtained will include determining whether the participant has any significant conditions or diseases that stopped at or prior to signing the ICF. Ongoing conditions are considered concurrent medical conditions (see Section 9.6.2).

Medication history information to be obtained includes any medication relevant to eligibility criteria stopped at or within 28 days before signing ICF.

9.1.3 Physical Examination Procedure

A physical examination performed by the Investigator or designee consists of the following body systems: (1) eyes; (2) ears, nose, throat; (3) cardiovascular system; (4) respiratory system; (5) gastrointestinal system; (6) dermatologic system; (7) extremities; (8) musculoskeletal system; (9) nervous system; (10) lymph nodes; and (11) other.

Any abnormal change from the baseline physical examination must be assessed as not clinically significant (NCS) or clinically significant (CS) by the Investigator and recorded in the source document and eCRF. Any CS change or new diagnosis as a result of a CS change, as determined by the Investigator, will be recorded as an AE in source documentation and on the AE eCRF described in Section 9.7.1.

